## 2. Use of the correct chemical disinfectant

Compliance with use of the correct chemical disinfectant will be calculated as a proportion:

- a. Numerator: Use of the correct chemical disinfectant
- b. Denominator: Number of rooms sampled

#### f. Potential confounders

## 1. Hand hygiene compliance

Hand hygiene compliance will be calculated as a proportion:

- a. Numerator: Number of times hand hygiene performed correctly
- b. Denominator: Number of hand hygiene observations

## 2. Room cleaning compliance

Room cleaning compliance will be calculated as a proportion:

- a. Numerator: Number of locations in a room from which a fluorescent marker was removed
- b. Denominator: Number of fluorescent markers applied to the room

## 3. Colonization pressure

Colonization pressure will be calculated as a proportion.

- Numerator: Number of patients with a current or prior (previous 12 months) infection or colonization with one of the four target MDROs during the calendar month.
- b. Denominator: Number of patients admitted to the hospital during the same calendar month

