## 6. DERIVED AND COMPUTED VARIABLES

## a. General strategy for aggregating data at the hospital level

All variables were collected and calculated during all four study phases at each study hospital. Variables were calculated and/or summarized for each of the disinfection strategies/phases individually.

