## c. Clinical incidence – Exposed Patients

1. Clinical incidence of MRSA, VRE, C. difficile, or MDRAB among exposed patients

The clinical incidence of all 4 target organisms (rate/10,000 exposure days) will be calculated for each study phase individually.

- a. Numerator: qualifying incident cases of any of the target organisms
- b. Denominator: exposure days for all exposures
- 2. Clinical incidence of *C. difficile* among exposed patients

The clinical incidence of *C. difficile* (rate/10,000 exposure days) will be calculated for each study phase individually.

- a. Numerator: qualifying incident cases of *C. difficile*
- b. Denominator: exposure days among patients exposed to *C. difficile* seed rooms

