## d. Clinical incidence – All Patients Admitted to the Hospital

Hospital-wide clinical incidence was calculated as the number of patients with hospital-acquired incidence of a target MDRO/10,000 patient days among patients who stayed in the hospital for at least 48 hours. Patients did not have to be "exposed" to a seed room to qualify for these analyses, though the same exclusion criteria were otherwise applied.

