## b. Adjustment for covariates

For the primary efficacy analysis, no covariates will be included for adjustment.

Important hospital- and patient-level parameters listed in Section 6f and 7 may be used as covariates in secondary analyses.

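### Colonization pressure, as Section 6f defines it, includes the trial's own incident cases, so an optional secondary model adjusted for it would pull the rate ratio toward 1

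*SAP*

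**What the plan says.** Section 6f lists three potential confounders: hand hygiene compliance, room cleaning compliance and colonization pressure. The numerator of colonization pressure, taken by calendar month, is "Number of patients with a current or prior (previous 12 months) infection or colonization with one of the four target MDROs" and its denominator is "Number of patients admitted to the hospital during the same calendar month". Nothing excludes patients who acquire the organism during the current stay, and there is no lag or pre-phase baseline.

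On timing, Section 6a states: "All variables were collected and calculated during all four study phases at each study hospital".

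The outcomes are counts of new cases. For the whole hospital, Section 6d uses the "number of patients with hospital-acquired incidence of a target MDRO/10,000 patient days". For exposed patients, Section 6c.1 gives "Numerator: qualifying incident cases of any of the target organisms".

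Section 11b keeps covariates out of the primary efficacy analysis, but says that important parameters "listed in Section 6f and 7 may be used as covariates in secondary analyses". The efficacy model in Section 8a contains strategy, study period and hospital.

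**The concern.** A patient found to have acquired a target organism in a given month is a patient with a current target organism in that month. Under the Section 6f.3 definition this patient is counted in the covariate as well as in the outcome. If a strategy prevents acquisitions, both fall together, and a model that holds the covariate fixed attributes part of the strategy's effect to lower pressure. The adjusted rate ratio moves toward 1.

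The order of strategies was randomised, and hospital and period are already in the model. The legitimate reason to adjust for pressure is therefore chance imbalance in imported burden. The definition mixes that burden with the outcome. At stake is the interpretation of any secondary model that uses the covariate: a real benefit could look smaller after adjustment for no reason other than how the covariate was built.

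**Working it through.** **1. Overlap by definition.** Every hospital-wide incident case (Section 6d) meets the numerator definition in Section 6f.3 in the month it is found. So does every exposed-patient case (Section 6c) found while the patient is in hospital. One limit applies: eligibility is organism-specific (Section 5b), whereas pressure counts carriage of any of the four organisms. An MRSA carrier who acquires VRE is already in the numerator and adds nothing to it.

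**2. Mechanical effect.** Let *s* be the share of the numerator made up of incident cases under the reference strategy, and RR the true rate ratio. The strategy then lowers the numerator by *s* × (1 − RR). For RR = 0.80 this is 0.10 × 0.20 = 2% at *s* = 10%, and 0.50 × 0.20 = 10% at *s* = 50%.

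**3. Anchor on the plan's own figures (Section 10b).** 959 events / 491,200 patient-days = 1.952 per 1,000 (stated 1.95). Power for two Poisson rates is Φ(|ln RR| / √(1/959 + 1/(959·RR)) − 1.96). This gives 61.2%, 92.7% and 99.6% for decreases of 10%, 15% and 20%, against the stated 60%, 92% and >99%. The planning figures reproduce, so they were used to set the event rate.

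**4. Simulation.** There were 9 hospitals × 4 periods in random order, with 959 events per 491,200 patient-days under the reference. The model was Poisson regression with strategy, hospital and period terms and a log patient-day offset, with 250 replicates per setting. Assumed, not in the SAP: *s* from 10% to 50%; SDs on the log scale of 0.4 (hospital), 0.1 (hospital-period) and 0.15 (imported burden); and a log-slope of imported burden on incidence of 0 or 0.5. Pressure was taken at hospital-period level.

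Each cell shows the mean rate ratio without pressure → with log pressure as defined, and the share of the log effect lost, 1 − ln(adjusted)/ln(unadjusted).

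| *s* | true 0.90, slope 0 | true 0.90, slope 0.5 | true 0.80, slope 0 | true 0.80, slope 0.5 |
|---|---|---|---|---|
| 10% | 0.896→0.897 (1%) | 0.892→0.898 (6%) | 0.798→0.800 (1%) | 0.795→0.807 (7%) |
| 20% | 0.899→0.903 (3%) | 0.905→0.915 (11%) | 0.800→0.809 (5%) | 0.801→0.824 (12%) |
| 35% | 0.901→0.914 (14%) | 0.905→0.928 (25%) | 0.798→0.825 (15%) | 0.801→0.849 (26%) |
| 50% | 0.900→0.932 (33%) | 0.899→0.942 (44%) | 0.799→0.859 (32%) | 0.797→0.877 (42%) |

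With incident cases left out of the numerator, the adjusted estimate stays within 0.002 of the unadjusted one in all 16 settings.

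A separate simulation of the same layout (400 replicates, true ratio 0.85) set incident cases at 10%, 20% or 30% of the prevalent pool. It gave 0.855, 0.870 and 0.882, a loss of about 4%, 14% and 23% of the log effect. The direction is the same. The 20% figure is above the 3-12% in the table, so the size depends on the set-up as well as on *s*.

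**5. Look-back against period length.** Periods last 7 months (Section 4a) and the look-back is 12 months. Even in the last month of a period the look-back covers 12 − 7 = 5 months of the preceding one. From the second period onward, cases acquired under an earlier strategy can therefore sit in the covariate. The simulations did not model this.

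**The case against.** The strongest reply is that no committed analysis depends on this definition. Section 11b keeps these variables out of the primary analysis and only permits them elsewhere, the Section 8a model does not contain them, and Section 11a promises caution in interpretation. This stands, and it limits the weight of the point.

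The reply is also right that the size is assumed. The SAP gives no incident share, and near 10% the shift is negligible. Exposed-patient cases are a smaller part of the numerator than hospital-wide cases: the reference-phase projections in Section 10 are 190 and 959, a ratio of 190/959 = 0.20. Direct overlap should therefore be much smaller for the exposed-patient outcomes.

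A reader might infer that adjusting for hand hygiene or room cleaning compliance removes effect in the same way, because both are measured during the phases among unblinded staff. The documents do not support this. Neither variable contains the outcome, nothing in the SAP says that the strategies change them, and without such a change any bias could be nil or go either way. With nine hospitals, chance imbalance in these practices is plausible, and optional adjustment for it is defensible.

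A reader might also expect an adjusted result to be presented as a stronger confirmation of the primary finding. The SAP does not say so.

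None of this answers the core: the definition has no exclusion for new cases, and Section 11b allows its use without restriction.

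**Conclusion.** The point holds for colonization pressure. Sections 6f.3 and 11b together permit adjusting an outcome for a variable that contains it and is measured under the strategy being tested. The direction, toward a rate ratio of 1, was the same in every setting run. The size is illustrative: about 1-7% of the log effect at a 10% incident share and 32-44% at 50%, under the assumed variances and slopes. It applies mainly to the hospital-wide secondary outcomes. It does not bias the primary analysis, and it is not a finding against hand hygiene or cleaning compliance as covariates. The wording should be corrected, but no planned primary conclusion rests on it.

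**What to change.** - For any adjusted model, define colonization pressure from carriage known at admission: positive within 48 hours of admission, or a history that predates the admission. An acquisition during the current stay then stays out of the numerator, while a patient who was already a carrier at admission is kept. Do not instead drop everyone who becomes an incident case. That would remove, for example, an MRSA carrier who later acquires VRE, and would again make the covariate depend on the outcome.
- Because the 12-month history outlasts a 7-month period, do not count as history a case acquired in the study hospital during an earlier study phase. Alternatively, use positivity at admission alone.
- State in Section 11b that any model adjusted for Section 6f variables is exploratory.
- Report hand hygiene and room cleaning compliance by strategy. Removing them from the covariate list is optional.

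Section 5b already separates patients by the 48-hour and 12-month rules, so the cost is SAP wording and minor extra data work. The downside is a less complete measure of pressure, since patients who acquire an organism in hospital are themselves a source.

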## g. Adverse outcomes

- 1. Room turnover time will be measured in minutes in two ways
  - a. Total turnover time calculated as the time from the room being declared dirty by bed control personnel to being declared clean by the environmental services personnel.
  - b. Cleaning time calculated as the time from the initiation of room cleaning to the room being declared clean by the environmental services personnel.
- 2. ED wait time calculated as the amount of time (minutes) between the ED physician's decision to admit the patient and departure from the ED
- 3. Diversion calculated as the number of hours the study hospital was on any form of diversion

# 7. STUDY CHARACTERIZATION ANALYSES

Demographic and comorbidities data will be described by study phase using mean (standard deviation) and median (IQR) for continuous variables and number (percent) for categorical variables. Comorbidity data will be obtained using enhanced ICD-9-CM code data obtained from administrative databases from study hospitals. The ICD-9 codes of interest will be used to calculate Charlson scores. Enhanced ICD-9-CM codes of interest are provided in Table 2.

Table 2. ICD-9-CM codes				
Comorbidities	Enhanced ICD-9-CM			
Myocardial infarction	410.x, 412.x			
Congestive heart failure	398.91, 402.01, 402.11, 402.91, 404.01, 404.03, 404.11, 404.13, 404.91, 404.93, 425.4-425.9, 428.x			
PVD	093, 437.3, 440.x, 441.x, 443.1-443.9, 447.1, 557.1, 557.9, V43.4			
Cerebrovascular disease	362.34, 430.x-438.x			
Dementia	290.x, 294.1, 331.2			
COPD	416.8, 416.9, 490.x-505.x, 506.4, 508.1, 508.8			
Rheumatic disease	446.5, 710.0-710.4, 714.0-714.2, 714.8, 725.x			
Peptic ulcer disease	531.x-534.x			
Mild liver disease	070.22, 070.23, 070.32, 070.33, 070.44, 070.54, 070.6, 070.9, 570.x, 571.x, 573.3, 573.4, 573.8, 573.9, V42.7			

Diabetes mellitus (uncomp)	250.0-250.3, 250.8, 250.9
DM complicated	250.4-250.7
Hemiplegia or paraplegia	334.1, 342.x, 343.x, 344.0-344.6, 344.9
Renal disease	403.01, 403.11, 403.91, 404.02, 404.03, 404.12, 404.13, 404.92, 404.93, 582.x, 583.0-583.7, 585.x, 586.x, 588, V42.0, V45.1, V56.x
Malignancy	140.x-172.x, 174.x-195.8, 200.x-208.x, 238.6
Mod/Severe liver disease	456.0-456.2, 572.2-572.8
Metastatic solid tumor	196.x-199.x
AIDS/HIV	042.x-044.x
Arrhythmias	426, 426.13, 426.7, 426.9, 426.1, 426.12, 427.0-427.4, 427.6-427.9, 785, 996.01, 996.04, V45.0, V53.3
Valvular disease	093.2, 394.x-397.x, 424.x, 746.3-746.6, V42.2, V43.3
Pulmonary circulation disease	415, 415.1, 416.x, 417, 417.8, 417.9
HTN uncomplicated	401.x
HTN complicated	402.x-405.x
Other neuro disorder	331.9, 332, 332.1, 333.4, 333.5, 333.92, 334.x-335.x, 336.2, 340.x, 341.x, 345.x, 348.1, 348.3, 780.3, 784.3
Chronic pulmonary disease	416.8, 416.9, 490.x -505.x, 506.4, 508.1, 508.8
Hypothyroid	240.9, 243.x, 244.x, 246.1, 246.8

#### 8. EFFICACY ANALYSES

# a. Analyses of clinical incidence - primary and secondary outcomes

Incidence rates will be compared between different disinfection protocols (study phases) using Poisson regression model with log of hospital-level number of "first positivity" cases as the outcome, log of hospital-level total days of exposure as an offset term and variables for intervention phase (B: quaternary ammonium + UV light, C: bleach, or D: bleach + UV light; A: standard disinfection will be used as reference), study period in the crossover sequence (1, 2, 3 or 4), and hospital as covariates. Interaction between intervention and study period will be evaluated. Generalized estimating equations (GEE) approach will be used to adjust for clustering by hospital. Individual models will be created for each primary and secondary efficacy outcome.

Each of the three enhanced terminal room disinfection strategies will be compared to the standard strategy; the null hypothesis in each case is that there is no difference in the clinical incidence rate between the enhanced strategy and the standard strategy. Each of the study phases will be compared to study phase A (reference) except for the patient-level analysis of *C. difficile*. As this comparison involved the comparison of bleach vs. bleach + UV-C for exposed patients, results from study phases B and D were compared to results from study phases A and C. Additional analyses will compare interventions using UV light vs those without UV light. In these analyses, variables for UV light (yes/no) and bleach (vs. quaternary ammonium) will replace the variable for intervention in the regression models.

The intention-to-treat (ITT) population will include all exposed patient stays, as described above. Per protocol (PP) population will exclude patient stays during study periods using UV light (phases B and D) if UV light was not documented as used before patient entered the room, or where the room was not in fact a seed room. For the purpose of the PP analysis, the UV device will only have to be turned on in the room; cycle completion will not be required for inclusion. Analyses of the outcomes for exposed patients will be conducted according to ITT and PP populations; analyses of the outcomes for the entire hospital will be conducted on ITT population only. Statistical tests will be performed at a two-sided significance level of 0.05 with no adjustment for multiple comparisons.

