## 4. STUDY METHODS

## a. Overall study design and plan

The study was designed as a pragmatic, prospective, multicenter, cluster-randomized, crossover trial with 2x2 factorial design to evaluate four different strategies for terminal room disinfection in nine study hospitals. The 28-month study period took place from April 2012 to July 2014. The 28-month period was separated into four 7-month study periods. Each study period consisted of a 1-month "wash in" period during which hospitals implemented and refined protocols followed by a 6-month period of data collection (Figure 1).

[figure not shown]

Figure 1. Schematic of crossover design. Each institution will randomly receive four interventions over the course of the 28-month study period. The first month of each intervention will be considered a "wash-out" month and surveillance data will not be counted (black boxes).

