## d. Randomization

Randomization occurred at the level of the hospital. All hospitals used each of the four strategies an equal amount of time. The order in which the four protocols were utilized was randomly assigned to each study hospital (Figure 3). Randomization was performed by random number generators for each hospital.

Hospital Study Phase 1 Study Phase 2 Study Phase 3 Study Phase 4 1 2 3 4 5 6 7 8 8 9 10 11 12 1 2 3 4 5 6 7 8 9 10 11 12 1 2 3 4 5 6 Month Year Wash In Quaternary ammomium except bleach for *C. difficile* rooms (Reference) Quaternary ammomium + UV except bleach + UV for *C. difficile* rooms Bleach Bleach + UV

Figure 3. Randomization scheme for 9 study hospitals

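### The SAP 8a GEE analysis rests on nine hospitals and names no small-sample method; the usual uncorrected Wald test would reject a true null about 14–21% of the time, not 5%

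*SAP*

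**What the plan says.** Section 4a describes a cluster-randomised crossover trial of "four different strategies for terminal room disinfection in nine study hospitals", and "The 28-month period was separated into four 7-month study periods". Section 4d adds: "The order in which the four protocols were utilized was randomly assigned to each study hospital".

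Section 8a fits a Poisson model to hospital-level case counts with exposure days as offset. Its terms are intervention (A as reference), "study period in the crossover sequence (1, 2, 3 or 4), and hospital as covariates". It continues: "Generalized estimating equations (GEE) approach will be used to adjust for clustering by hospital". A separate model of this kind is to be fitted for every primary and secondary efficacy outcome. On testing: "Statistical tests will be performed at a two-sided significance level of 0.05 with no adjustment for multiple comparisons".

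Section 8b adds overdispersed Poisson and negative binomial models as candidates, chosen by the smallest median squared deviation between predicted and observed rates. Section 11a promises p-values, estimates and 95% confidence intervals. Section 11b states: "For the primary efficacy analysis, no covariates will be included for adjustment".

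No section gives the working correlation, the type of standard error, the test (Wald or score), the reference distribution or a correction for few clusters.

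**The concern.** The empirical GEE variance is estimated from the spread of one score total per cluster. It is justified by a large number of clusters, and here there are nine. With so few, it is on average too small and also imprecise, and a normal reference distribution allows for neither. Tests then reject too often and intervals cover too seldom.

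Both primary endpoints and all secondary incidence endpoints use this one specification. A strategy with no effect could be reported as effective, or as harmful, about three times as often as the stated 5% level implies.

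**Working it through.** **Inputs from the SAP.** Nine hospitals × 4 periods = 36 cells (4a). With hospital categorical, the parameters are 1 intercept + 3 intervention + 3 period + 8 hospital = 15, leaving 36 − 15 = 21 residual degrees of freedom. Section 10 projects 190 baseline outcomes among exposed patients, so 4 × 190 = 760 under no effect. Hospital-wide it projects 959, so 4 × 959 = 3,836.

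**The plan's own figures.** The SAP gives no actual error rate for its GEE test, only the nominal 0.05. A two-Poisson-rate z test on 959 baseline events gives 61.2%, 92.7% and 99.6% power for 10%, 15% and 20% decreases, matching section 10 (60%, 92%, >99%). For exposed patients, 1,750 per strategy and 11% versus 8% give 85.7%, not the stated 80%, which is reached at a 2.8-point decrease. That mismatch does not bear on this point.

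**Assumptions not in the SAP.** Hospital size log-SD 0.6; between-hospital log-rate SD 0.3; hospital-phase coefficient of variation (CV) 0 to 0.4. The 400 and 120 event totals were chosen to represent rarer endpoints.

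**Formulas.** Let A = Σ μᵢxᵢxᵢ′ over the 36 cells, and let uₖ = Σ xᵢ(yᵢ − μᵢ) over hospital k's four cells.
- Uncorrected sandwich: V = A⁻¹(Σₖ uₖuₖ′)A⁻¹, Wald z = estimate/√V.
- Scaled Poisson: V = φA⁻¹, with φ = Σ[(yᵢ − μᵢ)²/μᵢ]/21.

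**Simulation.** The order of strategies is random for each hospital and there is no true effect. Each setting has 3,000 runs (107 unusable at 120 events). Monte Carlo error near 16% is 1.96 × √(0.16 × 0.84/3000) = 1.3 points. Rejection of B versus A at nominal 5%, hospital fitted:

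| Events, CV | Sandwich Wald z | Sandwich t(8) | Score test | Model-based z | Mancl-DeRouen t(8) | Scaled Poisson t(21) |
|---|---|---|---|---|---|---|
| 760, 0 | 14.7% | 9.4% | 4.7% | 4.4% | 3.2% | 4.4% |
| 760, 0.2 | 16.7% | 11.1% | 4.5% | 16.9% | 3.3% | 6.5% |
| 760, 0.4 | 17.7% | 12.5% | 4.4% | 37.3% | 3.7% | 7.4% |
| 400, 0.2 | 16.9% | 11.8% | 5.4% | 12.1% | 3.8% | 6.5% |
| 120, 0 | 16.4% | 11.2% | 5.5% | 5.2% | 2.9% | 4.8% |
| 3,836, 0 | 16.4% | 10.6% | 5.5% | 5.5% | 3.6% | 5.0% |
| 3,836, 0.2 | 20.1% | 13.9% | 5.5% | 44.3% | 4.4% | 8.7% |

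**Checks.**
- A separate GEE routine (800 runs per setting, error about ±2.5 points) gave 13.1–20.1% with hospital fitted, under independence and exchangeable working correlation.
- A further run gave 14.9–21.1% with z and 9.7–14.5% with t(8).
- A UV yes/no contrast with 60 cases per phase (assumed) gave 16.1%.

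**Why the error is this large.** At 190 cases per phase the mean estimated standard error was 72–78% of the true one. That shortfall alone moves the 1.96 cut-off to 1.96 × 0.72 = 1.41 or 1.96 × 0.78 = 1.53, with two-sided tails of about 16% and 13%. Imprecision of the standard error adds to this.

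**Is the hospital term responsible?** Without it the Wald z error at 760 events is 14.1% (CV 0) and 16.4% (CV 0.2), against 14.7% and 16.7% with it. It is not.

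**The case against.** The strongest reply is that the SAP never says it will use an uncorrected Wald z test. That stands. A reader might infer that the planned tests have an error of 14–21% outright, but the documents do not support this: on the same model and nine clusters a generalized score test holds 4.4–5.5%. The figure belongs to the usual implementation, which the SAP neither names nor excludes. A score p-value would still not repair the promised 95% intervals if these are built from the uncorrected empirical standard error.

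A second reply is that 8b already lists an overdispersed Poisson model. It does, but the choice among models depends on how well rates are fitted, which says nothing about whether standard errors are valid.

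Three further readings are tempting and do not hold:
- **Fitting hospital as a covariate causes the inflation.** The error is almost unchanged without it. With hospital fitted the 15 × 15 empirical covariance has rank 6, but that equals the 3 intervention and 3 period parameters, whose own block is of full rank.
- **GEE is pointless once hospital is in the model.** Hospital terms absorb differences between hospitals, not variation between phases within a hospital. At CV 0.4 model-based Poisson errors reject 37.3%, against 17.7% with the sandwich.
- **The chance that any of the three contrasts is falsely significant measures this defect.** It mixes variance bias with the absence of a multiplicity adjustment, which the SAP states openly.

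**Conclusion.** The concern holds in conditional form. Section 8a relies on GEE with nine clusters and fixes neither a test nor a correction. Under the usual uncorrected empirical-variance Wald z test, a nominal 5% comparison of one strategy with standard rejects a true null about 14–21% of the time, or about 10–15% with t on 8 degrees of freedom. In the same null settings, nominal 95% intervals based on z would cover about 100 − 21 = 79% to 100 − 14 = 86%.

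The exact size depends on hospital size spread, rate spread and hospital-phase variation, none of which the SAP gives, but the inflation appeared in every setting tried. The cause is the number of clusters.

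The model itself is also unsettled. Section 11b excludes covariates from the primary analysis, while 8a calls period and hospital covariates. The two agree only if these are regarded as design terms, which the SAP does not say.

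**What to change.** In section 8a, name the variance estimator, test and reference distribution, and use the same method for p-values and confidence intervals. Either of these would serve:

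1. GEE with a Mancl-DeRouen corrected sandwich and t on 8 degrees of freedom (about 3–4% error, slightly conservative). With hospital fitted the leverage matrix is singular, so state how it is inverted; a pseudo-inverse was used here.
2. The overdispersed Poisson model of 8b with intervention, period and hospital, scale not below 1, and t on 21 degrees of freedom. Runs with that floor gave 3.0–7.9%; the worst setting in the table is 8.7%. The hospital term must stay: without it, rejection at 760 events fell to 0.2% (CV 0) and 1.4% (CV 0.2).

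Fix this choice in advance rather than leave it to the fit criterion in 8b. Optionally confirm each primary p-value by a randomisation test that re-permutes each hospital's own sequence. In 250 trials it rejected 6.4%, compatible with 5% given a Monte Carlo error of 1.96 × √(0.05 × 0.95/250) = 2.7 points.

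Reword 11b to say that period and hospital are design terms in the primary model and that the exclusion concerns other covariates, or change 8a to match 11b.

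The cost is SAP wording and a few lines of code, with no new data. The price is wider confidence intervals.

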## b. Secondary endpoints:

- 1. First positivity Exposed patients. These secondary outcomes will include the clinical incidence of individual pathogens among exposed patients as determined by data obtained from microbiological laboratories in study hospitals.
  - a. Incidence of first positivity of MRSA among exposed patients
  - b. Incidence of first positivity of VRE among exposed patients
  - c. Incidence of first positivity of MDRAB among exposed patients
- 2. First positivity Entire hospital. These secondary outcomes will include the clinical incidence of target pathogens (collectively and individually) among all patients admitted to the study hospitals as determined by data obtained from microbiological laboratories in study hospitals.
  - a. Incidence of first positivity of BIG 4 for entire hospital
  - b. Incidence of first positivity of MRSA for entire hospital
  - c. Incidence of first positivity of VRE for entire hospital
  - d. Incidence of first positivity of CDI for entire hospital

e. Incidence of first positivity of MDRAB for entire hospital

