## 5. Clinical incidence of MDRAB among exposed patients

The clinical incidence of MDRAB (rate/10,000 exposure days) will be calculated for each study phase individually.

- c. Numerator: qualifying incident cases of MDRAB
- d. Denominator: exposure days among patients exposed to MDRAB seed rooms

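### SAP 8a has no rule for a strategy with zero cases: for exposed-patient MDRAB the rate ratio can diverge and a robust Wald test then rejects almost automatically

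*SAP*

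**What the plan says.** Section 4a describes a crossover to "evaluate four different strategies for terminal room disinfection in nine study hospitals", over four periods. Section 8a fits a Poisson regression with strategy (A as reference), "study period in the crossover sequence (1, 2, 3 or 4), and hospital as covariates". It adds that "Interaction between intervention and study period will be evaluated" and that "Generalized estimating equations (GEE) approach will be used to adjust for clustering by hospital". It then says "Individual models will be created for each primary and secondary efficacy outcome".

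Section 3b lists "Incidence of first positivity of MDRAB among exposed patients" as a secondary endpoint in its own right, and section 6c.5 narrows its rate base: "Denominator: exposure days among patients exposed to MDRAB seed rooms". MDRAB for the entire hospital is a further endpoint.

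One endpoint is treated differently. For *C. difficile* in exposed patients, "results from study phases B and D were compared to results from study phases A and C".

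Section 8b adds overdispersed Poisson and negative binomial models, chosen by closeness of predicted to observed rates. Section 11a allows nonparametric tests in general terms, without a trigger or a named method. Nothing says what happens when a strategy has no cases. The type of standard error, the working correlation and an expected MDRAB count are not given.

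**The concern.** A log-link model has no finite estimate for a strategy with zero cases. The fitted coefficient keeps falling until the iterations stop. If the Wald test divides that arbitrary number by a robust standard error of ordinary size, it declares a highly significant effect whatever the data support. If the reference strategy A is the empty one, all three contrasts diverge together in the other direction.

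The section 8b alternatives are normally fitted with the same link and diverge in the same way, and choosing among them by fit does not test whether the standard error is valid.

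At stake is a secondary claim that one strategy eliminated MDRAB, with a very small p-value, resting on a handful of cases spread by chance. Sections 8a and 11a apply no multiplicity adjustment that would temper it.

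**Working it through.** **Size of the model.** 9 hospitals x 4 periods = 36 counts in 9 clusters. Parameters: 1 intercept + 3 strategy + 3 period + 8 hospital = 15 (design rank confirmed as 15). A full strategy-by-period interaction adds up to 9, giving 24.

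**How many MDRAB cases? (assumption)** The SAP gives no figure. Section 10a projects 190 composite cases per strategy, so 4 x 190 = 760 with no effect. If MDRAB is 1-3% of these, that is 8-23 cases. Section 10b projects 959 composite cases hospital-wide per period: 4 x 959 = 3,836, and 1-3% is 38-115 cases.

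**Chance of an empty strategy.** With expected total m and equal exposure, a given strategy is empty with probability q = exp(-m/4). Some strategy is empty with probability 1 - (1 - q)^4, and A or B is empty with probability 1 - (1 - q)^2. The last column is the null simulation of the section 8a model (robust standard error, independence).

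| m | q | some strategy empty | A or B empty | B vs A falsely significant |
|---|---|---|---|---|
| 8 | 13.5% | 44% | 25% | 54% |
| 12 | 5.0% | 18% | 10% | 29% |
| 16 | 1.8% | 7% | 3.6% | 22% |
| 24 | 0.25% | 1% | 0.5% | 16% |
| 40 | 0.005% | 0.02% | 0.01% | 16% |

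Separate runs agree at the larger totals: 22-25% at 16 cases, 16% at 24 and 14-17% at 40.

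**What happens when a strategy is empty.** Null simulation: Poisson counts, uneven hospital shares, equal exposure, strategy order drawn at random for each hospital. Contrasts kept: no cases in an enhanced strategy, at least one in A.

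| m | median log rate ratio | median robust SE | robust, independence: p<0.05 | model-based SE, independence | robust, exchangeable: p<0.05 (no usable result) |
|---|---|---|---|---|---|
| 4 | -19.7 | 0.94 | 90% | 0% | 62% (27%) |
| 8 | -25.1 | 1.23 | 91% | 0% | 34% (54%) |
| 12 | -24.6 | 1.12 | 94% | 0% | 17% (76%) |
| 16 | -24.6 | 0.95 | 97% | 0% | 11% (84%) |

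The median estimate over the median standard error at m = 12 is -24.6/1.12 = -22, far beyond 1.96. A t reference with 8 degrees of freedom changes almost nothing (89%, 91%, 94%, 97%). In a further null run every contrast with B empty was rejected (45 of 45).

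**How much evidence such data hold.** With equal exposure and a cases in A against 0, the exact two-sided p-value is 2 x 0.5^a: 0.25 for 3 against 0, 0.0625 for 5 against 0, 0.008 for 8 against 0.

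**Candidate replacements under the null.** A re-randomisation test over the hospitals' strategy orders rejected in 1.6-4.4% at 8 to 40 cases. An exact binomial B versus A test rejected in 3% or less with pure Poisson counts. With assumed gamma variation between hospital-phases (squared coefficient of variation 1-4), it rejected in 7-18% at 16 cases, 12-27% at 24 and 20-38% at 40.

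**The case against.** Several points on the other side stand.

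- **Dependence on an unstated choice.** Section 8a names neither the standard error nor the working correlation, and model-based standard errors gave no false rejections. A reader might infer that no variance estimator helps; that is not so. Still, GEE is invoked to adjust for clustering, and under independence the model-based standard error makes no such adjustment, so the robust one is the natural reading. The model-based Wald test also errs the other way: at m = 16 the exact test found 20% of the same contrasts significant and the model-based test none.
- **Mechanism.** One might suppose that the robust standard error collapses to zero, or that 15 parameters are the cause. Neither holds. The standard error stays near 1, and without the hospital terms the rejection rate is 96-100%. For the same reason, the statement in section 11b that the primary analysis has no covariates offers no way out.
- **Not all the inflation is separation.** At 16 cases A or B is empty in only 3.6% of datasets, against 22% false rejection. Among datasets with no empty strategy, 37%, 23%, 23% and 17% were still rejected at 8, 12, 16 and 24 cases. That part comes from nine clusters and sparse counts.
- **Visibility.** A rate ratio near e^-20 would be noticed. Section 11a promises intervals and caution, and allows nonparametric tests. But with no trigger or method, the replacement would be chosen after the counts are seen.

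The stronger reading, that every endpoint faces a near-certain false result, is not supported. *C. difficile* in exposed patients has a pooled contrast. Hospital-wide MDRAB at 38 or more assumed cases has about a 0.03% chance of an empty strategy (q = exp(-38/4), four strategies). The other organisms are also unlikely to have one.

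**Conclusion.** The point holds in limited form. For a sparse single-organism outcome, realistically exposed-patient MDRAB, section 8a leads to a diverging estimate whenever a strategy has no cases, and neither section 8b nor 11a prevents it. Under robust standard errors with independence correlation, about 90-100% of such contrasts are falsely significant. Exchangeable correlation mainly exchanges false positives for fits with no usable result.

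How often this arises rests on the assumed case count. An empty strategy is quite likely at 8 cases (44%), uncommon at 16 (7%) and negligible at 40 (0.02%). Overall false rejection for B versus A falls from about 54% at 8 cases to about 16% at 24 and at 40, where it reflects few clusters rather than separation. The figures also assume equal exposure and Poisson counts.

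The primary endpoints are not affected by this mechanism. It is a secondary-endpoint defect with a cheap repair.

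**What to change.** Add to section 8a:

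1. State the type of standard error and the working correlation for all GEE models.
2. For any organism outcome with a strategy at zero cases, or with a total below a prespecified low number (for example about 20, where the chance of an empty strategy is 2.7%), do not report the GEE Wald p-value. Use a re-randomisation test over the hospitals' strategy orders, with the reference set matching how the orders were drawn under section 4d.
3. For those outcomes, give counts, exposure days and rates by strategy, with an interval that does not rely on the diverging estimate, and label the result exploratory.
4. Use an exact conditional Poisson test only if the plan explicitly assumes no overdispersion, since section 8b anticipates that overdispersion may occur.

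The cost is a few sentences and a short program, plus wide, conservative intervals for the rarest organism. The rule does not remove the inflation from nine clusters that remains at larger counts; that needs separate attention.
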